## 2.2 Secondary endpoints

- Clinical status according to a 3-category ordinal scale (resolution, non-resolution, death) evaluated on **days 7, 14 and 21**.
- Diagnostic hypotheses at inclusion and final diagnoses.
- Disease severity on **days 0, 7, 14 and 21**.
  - *in adults* :
    - Simplified ambulatory severity index (SAI)
    - Quick Sepsis Related Organ Failure Assessment (qSOFA)
  - *in children under 5 years of age*:
    - criteria of the algorithm for the management of childhood illnesses (ALMANACH)
- Initial and secondary hospitalization (assessed on **day 21**).
- Length of hospital stay (initial and/or secondary hospitalization) assessed on **day 21**.
- Number of secondary visits (assessed on **day 21**).
- Number and types of laboratory and radiology tests prescribed/actually performed.
- Number and types of medications and supportive care prescribed/actually administered.
- Detection of malaria by rapid test (HRP II antigen, pLDH antigen) and thick drop test (type and parasitemia)

## 2.3 Exploratory judgment criteria

- Frequency of bacteremia, with etiological distribution and drug resistance profiles antibiotics for identified germs
- Detection of dengue by rapid test (NS1 antigen, IgM)
- Detection and profiling of pathogens causing febrile illnesses by sequencing metagenomics

## 3. STUDY DESIGN

### **3.1 General study design**

This is a bi-centric, prospective, observational cohort study of adults and children in the presenting to the emergency department or outpatient clinic with a community-acquired febrile illness (with or without focal signs) at 2 clinical sites in the DRC. The study included blood sampling at inclusion for study analysis and storage. The study will describe the epidemiology, causes, clinical aspects and biomarker profile of the disease, the severity, management and outcome of febrile illnesses, using the data from collected during routine diagnostic and therapeutic procedures, and study analyses. Each patient will be monitored for 21 days. Follow-up will include:

- Daily visits for hospitalized patients,
- Telephone calls (or a visit to the study center or home visit) on days 7, 14 and 21 for outpatients and discharged patients.

## **4. PARTICIPANTS, POPULATION AND ELECTIONS**

### **4.1 Recruitment sites**

Kinshasa General Hospital (also known as Mama Yemo Hospital) is a 2,000-bed hospital, centrally located in the Commune de Gombe, serving an urban population. The pediatrics has 170 beds. Participants in the FIKI study will be recruited from the following departments pediatric emergencies, which currently see around 5 febrile children a day.

The Institut Médical Evangélique (IME) de Kimpese is the General Reference Hospital (HGR) of Kimpese, a 400-bed hospital in the province of Kongo Central, west of DRC. The department The pediatrics department has 64 beds, while the internal medicine department has 78 beds. Some of the participants in the FIKI study will be recruited there from emergency departments and the outpatient consultations. The monthly number of outpatient consultations and admissions to the HGR is of around 2257 and 167 respectively. Approximately 10% of patients seen at the outpatient clinic were present with fever.

The population served by this health facility is estimated at 187,796 (Zone de Santé de Kimpese). There are several health centers in this area. Recruitment will take place also, if necessary, in one or more of these health centers (selected on the basis of their proximity, attendance, clinical standards), by the study team based at the IME and following exactly the same study protocol.

### **4.2 Selection and recruitment**

The frequency of febrile illnesses can vary from season to season. In order to balance the seasonal recruitment, the FIKI study will be carried out in two phases staggering inclusions evenly over the duration of the study, to take account of these seasonal variations. Recruitment will be carried out in such a way as to avoid, as far as possible, any influence from members of the study team on the choice of participants to be included. Recruitment will be stratified by age and site, with the number of patients (adults and children) to be recruited defined for the 2 sites. This number will be evenly distributed over the duration of the study, with a recruitment target of

weekly. Participants will be recruited consecutively from the beginning of the week until the target is reached. If the planned number of patients has not been reached by the end of a week, the supplement will be paid the following week.

### 4.3 Inclusion and exclusion criteria

#### Inclusion criteria

- Fever in progress and objectified at presentation, or documented at home or in another location  
health care facility/24 hours of presentation defined by:  
*OR*
  - Oral or rectal temperature  $> 38^{\circ}\text{C}$*AND*
- Possibility of contact between the patient (or his or her designated relative) and the team responsible for
- study on days 7, 14 and 21.  
Informed consent signed by patient (adults) or legal representative acceptable (children or patients whose condition does not allow them to sign informed consent),

#### Exclusion criteria

with the consent of children aged 12 and over, wherever possible

- Children under two months old.
- Hospitalization  $> 48$  h in the last 14 days (to exclude nosocomial fevers).

### 4.4 Sample size

The sample size is of convenience and was adapted to the number of febrile patients. and feasibility forecasts. The sample size refers to the participants recruited in the laboratory phase of the study (following amendment 1 of the protocol). We plans to include 500 children in the HGK / Mama Yemo site, and 500 children + 500 adults in the HGR-IME and health centers in Kimpese. Sample size calculations can be found in section 6.3.

### 4.5 Withdrawal and termination of

#### the study

A participant may be withdrawn from the study if:

- The participant or legal representative withdraws consent
- The investigator believes that continued participation would have a negative effect on the health of the

Data from participants withdrawn from the study will be used until the time of the last visit. study.

In the absence of any news from a participant, the interviewer will do everything within his or her power to contact the participant.

(limited to a maximum of 3 calls to the available telephone numbers and/or visits spread over a number of days)

within the visit period (window of  $\pm 2$  days) to try to re-establish a connection with the participant for follow-up. A participant included in the study who however is no longer available for the follow-up visits will be considered as lost to follow-up/abandonment.

of the suspension and the reason(s) for the interruption or suspension. CEs will also be informed without delay and will receive from the sponsor or investigator/institution the reason(s) for interruption or suspension, as specified in the applicable regulatory requirements.

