#### **Follow-up visits**

After inclusion, each patient will be followed up for 21 days. Follow-up will include:

- Telephone calls (or visits to the study center or home visits by health agents) community) on days 7 (D5-9), 14 (D12-16) and 21 (D19-23) for patients followed in outpatients, discharged patients, or patients hospitalized in facilities other than the hospital inclusion site.
- Daily bedside visits for hospitalized patients

[figure not shown]
Every daily hospital visit (inpatients) and every visit or phone call whether planned or not, the study staff will collect the patient's symptoms and signs in the CRF. (type and severity), comorbidities, drugs and tests prescribed, medications received,

examinations performed, results of examinations, secondary visits and/or hospitalizations and the status (resolved, unresolved, dead).

After day 21, the investigator will establish a "final diagnosis", based on examination of the entire file. This final diagnosis will be syndromic and/or specific, according to standard definitions.

There are no laboratory procedures for follow-up visits.

Figure 1: Schedule of visits and clinical data collected\*.

\* For hospitalized patients, the same variables will be collected daily

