## **9.8 Insurance**

The coordinator of this study, the Institute of Tropical Medicine, obtained study insurance (without liability) to cover any injury, damage or loss suffered by study participants and which is caused directly or indirectly by their participation in the study.

Information on insurance is not specified in the GSI of this study, due to the fear that of unreasonable claims for compensation. In addition, we do not anticipate any physical injury or mental health problems as a result of participating in this event. observational (non-interventional) study.

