3.1. Final points of the study

Patients enrolled in the study will be monitored and evaluated at 4 points in time: at admission D0, at seventh follow-up day D7, at fourteenth follow-up day D14 and at twenty-first follow-up day D21. They will be categorized into 3 groups:

- **Resolution:** means (i) signs and symptoms have completely disappeared and treatment has been completed; or (ii) some signs or symptoms persist and/or treatment is still underway, but a marked improvement in these signs and symptoms suggests that the person will recover rapidly without the need for further investigation or treatment other than that already administered.
- **Non-resolution:** any combination other than those described for the "Resolution" option.
- **Deaths**

Patients with no clinical outcome (lost to follow-up, withdrawal of consent, etc.) will be excluded from analyses that include outcome. Additional sensitivity analyses will be carried out (section 4.5).

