4.2. Primary analysis

The proportion of survival with symptom resolution, assessed at day 21, will be estimated as a proportion. The numerator will be the number of survivors who meet the definition of resolved, and the denominator will be the number who have completed the visit by day 21. The 95% confidence intervals for the proportion will be estimated using Wilson's method. A worst-case sensitivity analysis will also be carried out, defining all missing outcomes at day 21 as deaths, to examine the robustness of the results.

CRP and WBC values at recruitment will be described and compared using descriptive methods (see section 4.1). Different variables will be explored to compare CRP and WBC values, including clinical outcome, age, site, severity, diagnosis and others.

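### Protocol 4.5 ends outcome collection when the investigator withdraws a participant on health grounds; the effect is probably small, but the missing day-21 outcomes are avoidable.

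*Protocol*

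**What the plan says.** Protocol 4.5 gives two grounds for withdrawal. One is withdrawal of consent by the participant or representative. The other is the investigator's judgement: "The investigator believes that continued participation would have a negative effect on the health of the" participant, where the available text breaks off. It then says: "Data from participants withdrawn from the study will be used until the time of the last visit". No later check of status is described for either group.

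On follow-up, protocol 5.1 says: "After inclusion, each patient will be followed up for 21 days". This means contacts on days 7, 14 and 21 by telephone, at the centre or at home, or daily bedside data collection for inpatients. It adds: "There are no laboratory procedures for follow-up visits". Section 9.8 calls this an "observational (non-interventional) study".

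On analysis, SAP 3.1 says: "Patients with no clinical outcome (lost to follow-up, withdrawal of consent, etc.) will be excluded from analyses that include outcome". For day-21 resolution, SAP 4.2 says that "the denominator will be the number who have completed the visit by day 21", and it adds a sensitivity analysis "defining all missing outcomes at day 21 as deaths, to examine the robustness of the results". SAP 4.6 leaves clinical status out of multiple imputation.

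**The concern.** In a treatment trial, a health-based withdrawal clause can spare a participant further exposure. Here the study blood is drawn once, at inclusion, and what follows is mostly asking how the patient is. Ending that enquiry removes almost no risk, but it loses the outcome. The patients concerned are plausibly sicker than average, so the loss would tend to raise reported resolution and lower reported death.

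At stake are the first primary endpoint and the day-21 death proportion. The Kaplan-Meier and Cox analyses in protocol 6.2 would also censor these patients at their last visit, for a reason that may be linked to prognosis. The plan itself creates this loss, in contrast to patients who cannot be reached.

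**Working it through.** **The plan's own precision figure.** Inputs from protocol 6.3: 500 per stratum, 20% drop-out, ±4.9 points.
- Evaluable n = 500 × 0.80 = 400.
- The documents give no expected proportion. At p = 0.5 the half-width is 1.96 × √(0.25/400) = 4.9 points (Wilson: 4.88). The stated figure reproduces.
- It covers random error only. At p = 0.90 the same formula gives 1.96 × √(0.09/400) = 2.9 points. At p = 0.04 it gives 1.96 × √(0.0384/400) = 1.9 points.

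**Bias from health-ground withdrawal.** The documents give none of the following, so all are assumptions: true day-21 death 4% and resolution 90%; a fraction w withdrawn on health grounds; mortality m among them; none of them resolved. Other losses are taken as unrelated to outcome.
- Reported death = (0.04 − w·m)/(1 − w)
- Reported resolution = 0.90/(1 − w)

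| w | Patients per 500 | Death, m = 30% | Death, m = 50% | Death, m = 70% | Resolution |
|---|---|---|---|---|---|
| 1% | 5 | 3.7% | 3.5% | 3.3% | 90.9% |
| 2% | 10 | 3.5% | 3.1% | 2.7% | 91.8% |
| 3% | 15 | 3.2% | 2.6% | 2.0% | 92.8% |

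For example, at w = 1% and m = 50%, death = (0.04 − 0.005)/0.99 = 3.5% and resolution = 0.90/0.99 = 90.9%.

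The shift in resolution equals 0.90·w/(1 − w). It reaches 4.9 points only at w = 0.049/0.949 = 5.2%.

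**How plausible are the larger rows?** The share of all deaths that would fall after an investigator withdrawal is w·m/0.04. This is 12.5% at w = 1% and m = 50%, 25% at 2% and 50%, and 52.5% at 3% and 70%. The last is hard to believe.

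**What the worst-case analysis shows.** Take 20% missing in total.
- If all of it is unrelated to outcome: resolution = 0.80 × 0.90 = 72.0%; death = 0.80 × 0.04 + 0.20 = 23.2%.
- If one point of the 20 is health-ground withdrawal (m = 50%): resolution = 0.80 × 0.90/0.99 = 72.7%; death = 0.80 × 0.035/0.99 + 0.20 = 22.8%.

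The two situations are almost indistinguishable. The bound is valid for day-21 resolution but says nothing about this particular loss. SAP 4.3 specifies no such analysis for days 7 and 14.

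**The case against.** A reader might infer that the clause by definition removes the sickest patients and so materially overstates survival. The text does not support that. The trigger is harm from participating, not worsening illness, and a patient whose infection progresses does not meet it. If observation can hardly harm anyone, the condition should seldom be met and w should be close to zero. The plan also follows sick patients closely: daily bedside status for inpatients, scheduled contacts for those hospitalised elsewhere, and relatives authorised to report up to day 21. These points stand. The link to severity is a reasonable inference and no more.

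The clause also has some content. Inclusion takes effect at signature, before a draw of up to 14.5 ml (under 14 years) or 30.5 ml, and patients without a telephone may be asked to travel to the centre. This is a good reason to keep the safety ground. It does not explain why status collection should end with it.

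Section 4.5 is incomplete in the available text, so a sentence on follow-up after withdrawal may have been lost. That lowers confidence. Against it, the surviving sentence on use of data points to stopping at the last visit.

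Finally, the worst-case analysis already bounds day-21 resolution, and SAP 3.1 excludes only patients who have no outcome. Both are true. The first cannot isolate this loss, and the second helps only if someone collects the outcome.

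**Conclusion.** The point holds in a limited form. Protocol 4.5 permits an avoidable loss of day-21 outcomes that is likely, but not certain, to be related to severity. The SAP then takes these patients out of the primary denominator without imputing their status.

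The effect is probably small. With 1% withdrawn and the assumptions above, it is about 0.9 points on resolution and 0.5 points on death, against half-widths of 2.9 and 1.9 points at those proportions. Death is the more sensitive in relative terms (4.0% to 3.5%). The results for 2% and 3% show direction and scale; they are not forecasts. The conclusion depends on assumed withdrawal and event rates, and on the surviving text of 4.5 being representative of the section. The documents do not support the further inferences that the primary result is seriously biased or that the safety ground should be deleted. The change is worth making because it costs little and no later analysis can recover an outcome that was not collected.

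**What to change.** Keep the safety ground in protocol 4.5 and add that, when the investigator invokes it, only study sampling or in-person contacts stop. Day-7, -14 and -21 status is still collected by telephone, from the authorised relative or from the hospital record, unless the participant or representative withdraws consent. Restrict the rule that data are used only to the last visit accordingly. Report withdrawals by reason and stratum, so that the size of this group is visible.

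SAP 3.1 needs little or no change, because it already keeps anyone whose status is obtained. Its pointer to section 4.5 for sensitivity analyses should go to 4.2, since 4.5 covers subgroups.

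The change uses the contact routes already in protocol 5.1 and adds no patients or scheduled visits. The cost is a short protocol amendment, which under section 9.2 may need approval from the ethics committees if it is judged substantial.

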## **5. STUDY PROCEDURES**

### **5.1 Study/visit schedule**

#### **Inclusion visit**

Participants will be included in the study as soon as the consent form has been signed. The study investigator or his or her representative will fill in the data collection form (box report form (CRF), the patient's demographic information, history, symptoms and signs (type and severity), co-morbidities, initial diagnosis, medications and examinations and his immediate decision (hospitalization or discharge).

The study team will work with patients to arrange the following contacts on days 7, 14 and 21.

- For patients with whom telephone contact is considered possible, the study team records the patient's telephone number and the number of the telephone number of one or more relatives authorized by the patient to provide information on health status up to day 21. Patients will also receive the member of staff responsible for the study.
- Patients for whom telephone contact is not an option will receive offer to return to the study center on days 7, 14 and 21. Home visits by community health workers participating in the study will also be considered if necessary and feasible.
- If the participant gives permission for the laboratory part of the study, a blood sample will be taken. (venous +/- capillary blood) is taken during the inclusion visit. This blood test is integrated with the routine sampling required for patient management. Immediate test results (CRP, white blood cell count with differentiation), blood cultures, thick drop, malaria RDT, dengue RDT) will be collected in the and some of them (hemocultures) communicated directly to the clinicians at study. Samples stored for further analysis (metagenomic evaluation) or of secondary research will be registered in the ITM biobank and the institutions research partners, depending on the logistical capacities being developed and well-established memorandums of understanding (based on existing collaborations).

#### **Follow-up visits**

After inclusion, each patient will be followed up for 21 days. Follow-up will include:

- Telephone calls (or visits to the study center or home visits by health agents) community) on days 7 (D5-9), 14 (D12-16) and 21 (D19-23) for patients followed in outpatients, discharged patients, or patients hospitalized in facilities other than the hospital inclusion site.
- Daily bedside visits for hospitalized patients

[figure not shown]
Every daily hospital visit (inpatients) and every visit or phone call whether planned or not, the study staff will collect the patient's symptoms and signs in the CRF. (type and severity), comorbidities, drugs and tests prescribed, medications received,

examinations performed, results of examinations, secondary visits and/or hospitalizations and the status (resolved, unresolved, dead).

After day 21, the investigator will establish a "final diagnosis", based on examination of the entire file. This final diagnosis will be syndromic and/or specific, according to standard definitions.

There are no laboratory procedures for follow-up visits.

Figure 1: Schedule of visits and clinical data collected\*.

\* For hospitalized patients, the same variables will be collected daily

## 5.2 Obtaining informed consent

Adults who agree to participate in the study, children's representatives who agree to the their child's participation and the representatives of adults whose condition does not allow them to sign the form.

informed consent (impaired consciousness, insufficient level of comprehension) is impaired and who agree to the patient's participation will be invited to sign the consent form after a oral explanation by a qualified professional. If a participant (or parent or representative) is unable to read or write, the signature of a witness to the informed consent discussion will be obtained.

For the witness, preference will be given to persons indicated by the patient or representative, or if not possible, it will be carefully checked that the proposed independent witness is worthy of ~~if the child is accepted by the patient~~ children aged 12 and over, the age at which the to give informed consent, will be asked to sign a consent form. consent (in addition to parental consent).

After the informed consent process, the form will be given to the patient or his/her representative. A patient with a disturbance of consciousness whose legal representative has given consent, will receive information about the study and will be asked to give formal consent when his or her condition is diagnosed.

will allow.

Informed consent and assent forms will be available in French, Lingala and English. (for Kinshasa) and Kikongo (for Kimpese).

The informed consent procedure will describe the (legitimate) purpose of the study, the procedures to be followed, the

risks and benefits of participation, and data management. Participants (or parents or representatives) will be informed that participation in the study is entirely voluntary and that the participant may withdraw from the study at any time without any negative consequences.

It will be explained to participants that the study and its laboratory procedures include a sample storage for secondary research (e.g. transcriptomics):

transcriptional profiling of peripheral blood to identify early biomarkers for distinguish bacteria from viral infections), and that these investigations can also include genetic analysis \*. Specific consent will be required for these analyses.

\*Note for the metagenomics protocol: unlike procedures with the intention host sequences, we do not consider the metagenomic protocol to be a "genetic analysis", as it aims to sequence, analyze and report RNA sequences rather than human sequences. However, since the technique is based on on the sequencing of all the RNA material present in the patient's sample, a small amount of material RNA of human origin will inevitably (incidentally) be sequenced in addition to the material pathogenic RNA. We will use laboratory and bioinformatics procedures to depleting human RNA sequences and enriching pathogenic sequences. Since this subtraction is not 100% efficient, some human sequences may remain in the the final data set used for pathogen identification. Some publishers can request free access to the raw data set.

For participants whose samples will be used for secondary research, which may include influence clinical management (e.g. important endemic infections such as trypanosomiasis, which is a severe disease that can remain asymptomatic for a long time), he will be explained that the medical team would be informed in the event of detection, so as to warn them.

They will

will then be advised to go to a nearby referral center, where a diagnostic evaluation will be carried out. (and possibly treatment) will be offered free of charge.

Similarly, patients will be informed that during metagenomic analyses and the secondary research, certain chronic infection diagnoses could be made in the same way. examples of HIV, or hepatitis B or C will be provided in the information form.

so that the participant fully understands what it's all about and what the implications are.

The consent process and documents will enable participants to give their consent only for the clinical and purely observational part, or to add a consent for (i) study laboratory analyses, (ii) sample storage for minimum of 10 years in the biobank for secondary research (iii) genetic analyses in secondary research. If participants give their permission for the storage of

samples, it will be explained that this consent for storage can be withdrawn at any time without having to provide any particular justification, and that at that time the patient's samples will be destroyed.

